## 2.5.1.2. METHOD OF RANDOMIZATION AND BLINDING

The sample will include 152 patients of both sexes and age range 19-70 years. Participants will be collected using the simple random sampling method and these meeting the inclusion and exclusion criteria will be recruited and will form the study sample. The participants will be allocated using the method of simple randomization with an allocation ratio of 1:1, i.e. in two equal groups of 76 people, each.

The randomization of patients to the A ATM group and the B A-S group will be performed with the help of a random number generator created in Stata software with the help of the "randomizer" package. The "randomizer" package through the principles of binomial distribution, randomly assigns to each participant their participation in either the intervention group or the active control group. In this way each participant will be placed in one of two groups at the start of the study and will remain in the same group for the duration of the study. The ratio of subjects between the two groups will be maintained at 1:1 throughout the study.

This study is a single blind clinical trial. The intervention will be perceived by the principal researcher, who will apply the treatment protocol in the intervention group (A ATM), the physiotherapist, who will apply the treatment protocol in the active control group (B A-S) and the participants. It is not feasible for both participants and therapists to be blinded, due to the nature of each intervention. All evaluations of the effectiveness of the treatment interventions will be carried out by two independent assessors who, although belonging to the research team of the study, do not know the type of intervention that each patient will receive, as well as the allocation of patients to the different treatment intervention groups (Kang, 2013, Opara *et al.*,

2013). The first assessor will administer the consent form, the demographic characteristics form, the questionnaires and recorded the primary outcome measures, as well as the secondary outcome measure prior to the start of the study. The second assessor will administer the compliance and complaint form to the participants and will record the primary outcome measure and the secondary outcome measures after the completion of the interventions. Data analysis will be performed by an independent biostatistician, an associate of the Musculoskeletal Physiotherapy Research Laboratory of the University of West Attica (UNIWA), who will not know the group in which each participant will have been allocated.

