#### 2.5.1.4. SAMPLING

The sampling of the study will follow the following steps. Starting on July 25, 2022 and until the required number of people set according to the protocol is completed, the doctors of the pain clinic of the 1st Anesthesiology Clinic of the Aretaeio hospital will assess all the patients who will come to the outpatient clinics and will be diagnosed by them with chronic non-specific neck pain or will have already a diagnosis of chronic non-specific neck pain by their treating physician. The

assessment of the patients will be carried out according to the inclusion and the exclusion criteria that will be defined in this study.

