# 2.8. PROCEDURE

Initially, the prospective participants who will come from the structures mentioned in the section "Conducting research - Declaration of consent" will send through their electronic mail or by hand their medical diagnosis. The latter, combined with the exclusion criteria set, will be the way to sort the appropriate population. Participants will complete their consent form and demographic information. A full musculoskeletal assessment by an experienced physical therapist trained in the identification of myofascial pain trigger points (MTrPs) will be required at the start of the A-S group protocol. The determination of each MTrP will be achieved by palpation of the muscles under examination - upper trapezius and levator scapulae - based on the criteria of Travell and Simons (1992). The points will be marked with an indelible ink and recorded on a body chart. The skin will be cleaned with alcohol before the start of the intervention. The ATM technique requires no preparation.

During the intervention period (five weeks) the exact protocol will be followed, as analyzed in the corresponding subsections "Group A-ATM (FM)" and "Group BA-S". Acupuncture sessions will take place in the Pain Clinic of the Aretaeio hospital and will be carried out at ambient temperature (25°C) as the reduced temperature causes vasoconstriction making it difficult to apply acupuncture. The treatment area

will be quiet, sunny and clean. The two interventions will take place in the morning and afternoon, from 8.30 am to 6.30 pm.

Measurements will be carried out at the time points before the start of the intervention, after completion and at the follow-up at four months. In detail, PPT, ROM of flexion-extension, rotation and side flexion and neck position sense, respiratory function and flexor muscle strength will be recorded while patients will complete all seven questionnaires. From the total sample number, the patients participating in the follow-up will be calculated and therefore the cumulative dropout rate will be derived, which will be allocated to the two groups. Those who do not successfully complete treatment will be asked about the reasons that contributed to this. Finally, adverse effects from the application and/or ATM will be recorded.

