# 2.9. STATISTICAL ANALYSIS

Quantitative variables will be expressed as mean and standard deviation (SD). Qualitative variables will be expressed as absolute (N) and relative (%) frequencies. Pearson's  $\chi^2$  test and Fisher's exact test (where it is necessary) will be used to compare proportions, as well as McNemar test will be used to compare the percentages of kinesiophobia between measurements. Student's t-test or nonparametric criterion Mann-Whitney will be used for the comparison of the quantitative variables between the two groups. The change in the used scales and other indicators of the participants over time will be tested using linear mixed models from which dependence coefficients ( $\beta$ ) and their Standard Errors (SE) will be obtained. The group, the measurement (endline vs baseline) and their interaction term (to be tested in which extent the change is different between measurements in the two groups), will be introduced as independent variables. In the cases, where the interaction term will be found significant, sex, age, BMI and the symptoms duration will be introduced in the model (the chosen confounding factors are the most significant), in order to be tested if the interaction remain significant. Moreover, in the case that measurements at some outcome measures will be found to differ significantly at the initial measurement between the two groups, a result not due to systematic error but found to be due to random sampling. In these cases, their initial values will be entered into the mixed linear models as an independent variable to ensure that the findings from the models are not due to the initial differences between the groups. In cases that will be found significant differences between baseline measurements, between the two groups, the initial measurements will be introduced in linear mixed models as independent variable, in order to be ensured that the findings from these models are not due to initial differences between the groups. All reported p values will be two-tailed and statistical significance will be set at p < 0.05. Analyses will be conducted using the IBM SPSS Statistics 26.0.

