## 2.11. DISCUSSION

In the discussion the results will be recapitulated, analyzed and related to the existing literature. Each studied parameter of each research question will be assessed separately and the correlation based on the results obtained from the existing literature, which will be listed in the general part, will be highlighted. If the hypothesis is verified, then it will be compatible with the findings of the studies so far. Otherwise, it is against them. Finally, the above will be interpreted and the reason will be justified.

The aim of each study is to minimize the limitations, in order to draw safer conclusions and then to generalize the results.

The sample will consist of a wide age and social spectrum, which provides more reliability to the study and increases the power of the FM, giving the possibility of its application without limitations. Furthermore, a wide variety of parameters will be evaluated in a large sample size, providing the possibility of deriving statistically significant results. The number of the participants is satisfactory and larger than that of the majority of studies analyzed in the literature review. Additionally, recording the compliance rate is an additional advantage and is not included in the most studies.

In the limitations is included the design of the study, which is a 'single-blind' method, eliminating systematic error for the observer. Another limitation is represented by the heterogeneity in the severity of the patients' symptoms, which could be specified in the inclusion criteria. Also, the plethora of exclusion criteria, that were set due to the acupuncture may constitutes an obstacle to the promotion of the results in the general population. Last but not least, short-term or long-term follow-up will not be conducted.

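### The plan claims simple random sampling but describes non-random clinic recruitment; its advance explanation of baseline differences and its claim of unrestricted application also need correcting (minor)

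*Combined protocol and SAP*

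**What the plan says.** Four places bear on how the sample arises and what may be inferred from it.

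- **Section 2.5.1.2 (randomization and blinding)** gives the sampling method: "Participants will be collected using the simple random sampling method". Its next sentence deals separately with allocation, by simple randomization in a 1:1 ratio.
- **Section 2.5.1.4 (sampling)** describes the recruitment. Physicians at a hospital pain clinic "will assess all the patients who will come to the outpatient clinics", provided they have the diagnosis. This begins on a set date and goes on "until the required number of people set according to the protocol is completed". Section 2.8 (procedure) gives a second account, with "the prospective participants who will come from the structures mentioned in the section" on conduct and consent. That section, 2.5.1.3, names a municipal centre as well as the hospital pain clinic.
- **Section 2.9 (statistical analysis)** describes a significant baseline difference between the groups as "a result not due to systematic error but found to be due to random sampling". In such cases it then enters the initial value into the linear mixed model.
- **Section 2.11 (discussion)** says that the wide age and social range of the sample strengthens the Feldenkrais method, "giving the possibility of its application without limitations". Later in the section it says that the many exclusions made because of the acupuncture "may constitutes an obstacle to the promotion of the results in the general population".

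**The concern.** Simple random sampling has a definite meaning: a list of the population, and a draw in which each member has the same known chance of selection. A reader who takes the term at face value will think the sample represents a defined population of people with chronic neck pain. If the sample is in fact whoever attended and agreed, that inference is not available.

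The matter is more than terminology because research question 1 is a before-after comparison within the ATM arm and has its own main hypothesis. Randomisation does not protect that comparison, so what it means depends heavily on who was recruited.

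The sentence in section 2.9 raises a different issue. A plan cannot know beforehand why the groups will differ at baseline, and sampling has no bearing on whether the two arms are comparable. The sentence in section 2.11 raises a third: a claim about the reach of the findings that its own section goes on to qualify.

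**Working it through.** The point rests on text, so the main check sets the sections side by side. The plan gives no figure to reproduce.

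**1. Sampling.**

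| Feature of simple random sampling | What the plan describes |
|---|---|
| A sampling frame | None in any section |
| A random draw from it | None: all attenders with the diagnosis are assessed (2.5.1.4), and all who remain after the criteria are applied complete the consent form (2.5.1.6) |
| A sample drawn from a fixed list | Recruitment runs from a start date until the number is reached (2.5.1.4) |
| A defined source | One hospital pain clinic (2.5.1.4), or structures in the plural, with diagnoses sent by e-mail or by hand (2.8); a physician's referral is required (2.5.1.3) |

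Section 2.5.1.4 describes consecutive recruitment. The phrase in section 2.5.1.2 cannot be a slip for random allocation, because the next sentence covers allocation.

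**2. Baseline differences.** Between two randomised arms, chance differences come from the allocation, however the participants were found. To see how often they would arise, take the two-sided 0.05 level of section 2.9 and suppose *k* independent baseline tests. Independence is an assumption; these outcomes are likely to be correlated.

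- Expected number of significant differences = 0.05*k*. Probability of at least one = 1 − 0.95^*k*.
- *k* = 11 (one per outcome in the section 2.3 hypotheses): 0.05 × 11 = 0.55 expected; 1 − 0.95^11 = 1 − 0.569 = 0.431, or 43%.
- *k* = 22 (assumed, two measures per outcome): 0.05 × 22 = 1.1 expected; 1 − 0.95^22 = 1 − 0.324 = 0.676, or 68%.

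One or two significant differences would therefore be unremarkable under sound allocation, and chance is a fair default explanation. It is still a default, not a finding. What supports it is the conduct of the allocation, not the sampling and not a sentence written beforehand.

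**3. Generalisation.** Table 2 in section 2.5.1.6 lists 24 exclusion criteria. At least four concern needling: skin damage or wounds in the puncture area, a previous adverse reaction to acupuncture, metal allergy, and fear of needles. These have no evident relation to ATM, so the trial is silent on ATM in such patients. The documents do not give the share of neck-pain patients removed by any criterion, so the size of the selection cannot be computed.

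**The case against.** The case for leaving the plan alone is that non-random recruitment is ordinary in trials, does not bias a randomised comparison, and changes no test, sample size or estimate here. Eligibility is defined, the clinic is named, and the exclusions are already listed as a limitation. All of that stands, and it is why the point is minor.

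A reader might infer four stronger things that the documents do not support.

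- *That the sampling claim is what justifies unrestricted application.* Section 2.11 rests that claim on the wide age and social range and does not mention random sampling. It is a separate overstatement.
- *That section 2.9 relies on section 2.5.1.2.* The only link is shared wording. Section 2.3 uses similar language for chance in general, so section 2.9 may loosely mean chance under allocation. Its sentence is also grammatically incomplete and could be read as a condition.
- *That section 2.9 merely excuses imbalance.* It says twice that the initial value will be entered into the model, though only after a significant difference.
- *That everyone comes from one clinic.* Section 2.8 leaves the source unsettled.

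The objection does not remove the contradiction over sampling. Nor does it rescue the attribution in section 2.9: even read as chance under allocation, the wording excludes systematic error before the allocation has been carried out.

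**Conclusion.** The concern holds in three separate parts. First, the simple random sampling stated in section 2.5.1.2 does not exist in the design, and the recruitment source is itself inconsistently described. Second, section 2.9 excludes systematic error as a cause of baseline differences in advance, which neither sampling nor a prior statement can establish. Third, the claim of unrestricted application in section 2.11 conflicts with the limit conceded in the same section.

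It would be wrong to conclude that the ATM versus acupuncture-stretching estimate is biased by the way patients were recruited; the randomised contrast is unaffected. What is affected is the population to which the conclusions apply, most directly for the within-arm question. No magnitude can be attached to this from the documents. The 43% and 68% figures show only that chance imbalance is likely, and they rest on the assumed number and independence of the tests. Severity: minor.

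**What to change.** - **Sections 2.5.1.2, 2.5.1.3, 2.5.1.4 and 2.8.** Reconcile them on where participants come from. Replace the sampling claim with a description of a non-random sample: consecutive eligible attenders of the named source or sources. Record and report how many patients were screened, excluded (by criterion) and declined.
- **Section 2.9.** Delete the advance attribution and refer instead to chance imbalance under random allocation. Use the baseline value in every between-group model, not only after a significance test. State the form of the model, because the baseline measurement is already one of its two responses. With complete data, adding it again as a main effect leaves the estimated group-by-measurement interaction unchanged. A simple alternative takes the post-treatment value as the response, with group and baseline value as predictors.
- **Section 2.11.** Limit the generalisation to patients eligible for both arms at the recruiting source or sources.

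The cost is rewording in these sections, a simple screening log and a narrower claim. The sample size and the visits do not change.

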# 2.5. MATERIAL AND METHOD

## 2.5.1. SAMPLE

## 2.5.1.1. SAMPLE CHARACTERISTICS

During the initial calculation of the sample number, the number of the participants was determined, with purpose, the method of Analysis of Variance (ANOVA) in two groups of equal population, to identify a standardized effect size equal to 0.25 with a power of 80% and a level of statistical significance of 5%. The standardized effect size is defined as follows: Let the measurement tool X and groups A, B and  $\mu$ A,  $\mu$ B

be the mean values of X in groups A and B. SD is the Standard Deviation of X in the whole population. The effect size is given by the formula  $(|\mu A-\mu B|)/SD$ . The calculation was performed with the program G\*power version 3.1.9.7\* and the necessary sample size was calculated at 126 subjects. According to the relevant literature, similar standardized sample sizes have been used in two studies dealing with chronic neck pain (Lundblad *et al.*, 1999; Malmgren-Olsson *et al.*, 2009). Moreover, a dropout rate of 20% was expected, so a final number of around 152 patients is realistic for this study.

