According to the philosophy of FM, the treatment of chronic neck pain requires an approach from the perspective of other components besides the cervical spine. In this light, neck pain can originate from the neck but also from other causes, including inadequate breathing patterns, pelvic tilts, insufficient differentiation of eye or head movements, overuse of the upper extremity musculature. An inseparable relationship is detected between the neck and the temporomandibular joint, i.e. the incorrect position of the former affects the function of the latter and conversely the increased tension in the temporomandibular joint changes the muscle tone of the neck. This category also includes the limited movement of the lumbar spine as well as the injury of the end of the foot that disrupts the smooth functioning of the biokinetic chain (Plastaras *et al.*, 2011).

In the A ATM group (intervention group) the ATM technique will be applied in group sessions (6-8 patients) by a physiotherapist, specialized in the FM with at least five years of experience. The ATM protocol will be implemented in ten sessions, two per week, of 50 minutes each, for a period of 5 weeks.

On the remaining days, home exercises will be given to the patients in the form of printed illustrated instructions for their correct execution. These ATM exercises, will be a repetition of the ATM lesson that they will have been taught and, will be performed once a day, until the next session, where participants will learn and implement the next ATM lesson. The execution rate of the movements and the movement pattern will be individualized, as they dependent on each patient.

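### Simple (binomial) randomisation does not guarantee the two equal groups of 76, or the 1:1 ratio held throughout, that the same section promises

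*Combined protocol and SAP*

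**What the plan says.** Section 2.5.1.2 makes three statements about allocation.

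- **Method and result.** Participants will be "allocated using the method of simple randomization with an allocation ratio of 1:1, i.e. in two equal groups of 76 people, each".
- **Mechanism.** The Stata package "through the principles of binomial distribution, randomly assigns to each participant their participation in either the intervention group or the active control group".
- **Ratio over time.** "The ratio of subjects between the two groups will be maintained at 1:1 throughout the study".

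The total comes from the same section: "The sample will include 152 patients of both sexes and age range 19-70 years". Section 2.5.1.1 bases the sample size on the "method of Analysis of Variance (ANOVA) in two groups of equal population". No section mentions blocks, stratification, minimisation, a list with fixed counts per arm, or any other restriction.

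**The concern.** The named method and the promised result belong to different kinds of randomisation. If each patient is assigned by a binomial draw, the final arm sizes are random and so is the running difference during recruitment. Fixed counts per arm and a ratio held during accrual are properties of restricted randomisation.

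As written, the section can be followed in two ways that lead to different trials. One accepts whatever split chance gives, which departs from the stated 76 per arm. The other achieves equality by some means the documents do not describe. If the trial ended at 76/76, a reader could not tell whether this came from chance, an undisclosed restriction or a later adjustment. The therapists in both arms know the treatment, and the principal researcher delivers one of them, so the allocation procedure needs to be unambiguous.

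**Working it through.** **Inputs**
- Total randomised: 152 (section 2.5.1.2).
- Assignment probability: 0.5, assumed from the 1:1 ratio. The documents do not give the package settings.
- Effect size 0.25, power 80%, significance level 5% (section 2.5.1.1), two-sided (section 2.9).
- Dropout: 20% (section 2.5.1.1).

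**1. The plan's own figures.** Reading 0.25 as Cohen's f gives a standardised mean difference d = 2 × 0.25 = 0.50. The normal approximation then gives, per arm,

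n = 2 × (1.960 + 0.842)² / 0.50² = 62.8, rounded up to 63, so 126 in total.

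126 × 1.2 = 151.2, rounded up to 152, and 152 / 2 = 76. The stated 126, 152 and 76 therefore reproduce on this reading.

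**2. Arm size under the described mechanism.** Let X be the size of one arm, X ~ Binomial(152, 0.5).
- Standard deviation: √(152 × 0.25) = 6.16.
- P(X = 76) = C(152, 76) / 2¹⁵² = 0.0646, so the arms are unequal in 93.5% of trials.
- The 2.5% and 97.5% quantiles are 64 and 88.
- A difference of 10 or more needs X ≤ 71 or X ≥ 81: 2 × P(X ≤ 71) = 0.466.
- A difference of 20 or more needs X ≤ 66 or X ≥ 86: 2 × P(X ≤ 66) = 0.123.
- The mean absolute difference between arms is 9.8 patients.

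**3. Power cost.** With 80% retention, 152 × 0.8 = 121.6, taken as 122 completers. An even split is 61/61. A 64/88 split scales to 51.2/70.4, taken as 51/71 to keep the same total. Power is from the non-central F distribution with noncentrality d² × n₁n₂/(n₁ + n₂), at the two-sided 5% level.

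| Assumed d | Noncentrality 61/61 | Power 61/61 | Noncentrality 51/71 | Power 51/71 |
|---|---|---|---|---|
| 0.50 (0.25 read as Cohen's f) | 7.625 | 78.2% | 7.420 | 77.1% |
| 0.25 (as section 2.5.1.1 defines it) | 1.906 | 27.8% | 1.855 | 27.2% |

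Both values of d are shown because section 2.5.1.1 defines the effect as the mean difference divided by the SD, whereas the stated 126 fits only d = 0.50. That discrepancy is a separate matter. On either reading, an imbalance at the edge of the 95% range costs about 1.1 points or less (78.2 − 77.1 = 1.1; 27.8 − 27.2 = 0.6).

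**The case against.** The strongest reply is that nothing is wrong with simple randomisation. It is unbiased, it is the hardest scheme to predict, and neither the mixed models nor the t-tests of section 2.9 need equal arms. The power loss is trivial. All of that stands, and this point does not rest on bias or power.

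A second reply is that 1:1 is only a target probability. That would do for the ratio alone. It does not fit a text that gives head counts per arm and says the ratio of subjects will be maintained.

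A third is that the wording may loosely describe a list with fixed counts, since the package settings are not shown. That is possible. The documents therefore establish contradictory wording, not that the scheme in use is unrestricted.

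Three stronger readings are tempting, and the documents do not support them.

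- **That the method cannot produce 76/76.** It can, by chance, in 6.5% of trials. It does not guarantee it.
- **That staff will have to override the list near the end.** If equality were enforced by hand, the last allocations would become predictable to anyone who knew the running count. The documents do not say this will be done, and do not exclude it. Unequal arms could simply be accepted, or a fixed-count list prepared beforehand.
- **That runs to one arm will disrupt the ATM classes.** Section 2.5.2.1 gives only "group sessions (6-8 patients". Without a recruitment rate, a class schedule or a waiting rule, no such effect can be shown.

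**Conclusion.** The inconsistency is real and lies within section 2.5.1.2: the named method does not secure the stated equal groups or the maintained ratio. The size of the gap is 6.5% for an exact 76/76 split, a 95% range of 64 to 88 for one arm, and differences of at least 10 and at least 20 patients in 47% and 12% of trials. These figures assume independent assignment with probability 0.5 and exactly 152 randomised.

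The consequence is modest. Validity is not threatened, and the loss of power is about one point at most within that range, under the assumed d and 80% retention. A reader might infer that the comparison is biased or that concealment has been broken; nothing in the documents shows either. The case for changing the text is that it promises a property its method lacks, and the correction costs very little.

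**What to change.** Preferred: replace simple randomisation with a restricted list generated in advance, for example permuted blocks of randomly varying size. Someone outside treatment and assessment should hold the list and release each allocation only after consent and baseline measurement. With blocks, the running difference never exceeds half the largest block, so the scheme gives the near-equal split and running 1:1 ratio that the text promises. The cost is one changed command and one paragraph. The downside is that allocations at the end of a block are slightly easier to guess; varying the block sizes and not disclosing them limits this.

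Alternative: keep simple randomisation, delete the statements of 76 per arm and of a maintained 1:1 ratio, and state that arm sizes will vary, with a 95% range of 64 to 88 at 152 randomised. This costs a few sentences. If a restriction is already in use, naming it in section 2.5.1.2 in place of the simple, binomial description resolves the contradiction.
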